10.2. TREATMENT COMPLIANCE

A descriptive summary will be provided for the count and percentages of subjects with each of the following at any infusion visit:

- Planned doses that were not administered completely
- Infusion interruptions

Summaries will be provided by treatment received in HZNP-TEP-301 and overall. A separate summary will also be provided by subject enrollment type (subjects who were proptosis non-responders in HZNP-TEP-301, subjects who relapsed during the Follow-Up Period in HZNP-TEP-301).

10.3. ADVERSE EVENTS

All adverse events will be coded using MedDRA version 20.1. The TEAE reporting period begins with administration of the first dose of study medication on HZNP-TEP-302 Day 1 and continues until 3 weeks (21 days) after the last dose of study drug. The Follow-Up AE reporting period begins 3 weeks (21 days) after the last dose of study drug through completion of the Follow-Up Period (Week 48 or PW).

Missing data conventions for AEs are described in Section 6.3.4.

An overall summary of TEAEs will be provided by treatment received in HZNP-TEP-301 and overall, including the number and percentage of subjects with each AE type as well as the number of events for each of the following:

- TEAEs

- Serious TEAEs
- Related TEAEs
- Related serious TEAEs
- TEAEs with an intensity of severe or higher
- TEAEs leading to interruption of study drug administration
- TEAEs leading to permanent withdrawal of study drug
- Related TEAEs leading to permanent withdrawal of study drug
- TEAEs leading to study discontinuation
- Related TEAEs leading to study discontinuation
- TEAEs leading to death

Additional TEAE summaries will be provided by treatment received in HZNP-TEP-301 and overall, including the number and percentage of subjects experiencing TEAEs for the following:

- TEAEs overall and by SOC and PT, including the following subgroup analyses:
 - Age (<65 years, ≥65 years)
 - Gender (male, female)
 - Race (white, black or African American, Asian, other)
 - Ethnicity (Hispanic or Latino, not Hispanic or Latino)
- Related TEAEs overall and by SOC and PT
- TEAEs by maximum intensity, overall and by SOC and PT
- Serious TEAEs, overall and by SOC and PT
- Related TEAEs by intensity, overall and by SOC and PT
- TEAEs leading to permanent withdrawal of study drug, overall and by SOC and PT

- TEAEs of special interest including potential infusion-related reaction, anaphylactic reaction, hearing loss, hyperglycemia, muscle spasm, and diarrhea (see Section 10.3.1), by SOC, PT and overall
- TEAEs of special interest with missing AE start times including potential infusion-related reaction of any type, infusion-related reaction excluding those of an anaphylactic nature, and anaphylactic reactions (see Section 10.3.1), by SOC, PT and overall

For summaries by SOC, PT, and maximum intensity, a subject will only be counted once for each SOC based on the maximum intensity level reported for that SOC and once for each unique PT within that SOC level at the maximum intensity level reported for that PT. For summaries by SOC and PT only, a subject will be counted at most once at the SOC level and at most once at each unique PT within the SOC level. Summaries presenting the frequency of TEAEs by SOC and PT will be ordered alphabetically by SOC and then, within a SOC, alphabetically by PT.

The aforementioned summaries will be repeated for AEs occurring during the Follow-Up Period with the exception of AEs leading to permanent withdrawal of study drug. Denominators for the Follow-Up Period AE summaries will be based on the number of subjects entering the Follow-Up Period (i.e., complete or discontinue study after Week 24/last treatment).

In addition to a listing of all AEs, separate listings will be provided for serious AEs, AEs leading to withdrawal of study drug, AEs leading to study discontinuation, AEs of special interest, and AEs leading to death. TEAEs will be identified on each listing.

10.3.1. Adverse Events of Special Interest

Adverse events of special interest will be identified as follows:

- Potential infusion-related reactions: TEAEs that occur within 2 hours after initiating infusion
- Anaphylactic reactions: TEAEs that occur within 2 hours after initiating infusion and meet any one of the 3 criteria from Section 2.6.3 of the Introductory Guide for Standardised MedDRA Queries (SMQs) ([MedDRA, 2017](#)):
 - A narrow term or a term from Category A
 - A term from Category B AND a term from Category C
 - A term from Category D AND [a term from Category B OR a term from Category C]

- Hyperglycemia: TEAEs by any PTs under the SMQ “Hyperglycaemia/new onset diabetes mellitus” (narrow).
- Muscle spasm: TEAEs by the PT “muscle spasm”
- Diarrhea: TEAEs by any PTs under the SMQ “Noninfectious diarrhea” (broad search)
- Hearing loss: TEAEs by any PTs under the SMQ “Hearing impairment” (a sub-SMQ under “Hearing and vestibular disorders”) and HLT “Hearing losses”
- Potential infusion-related reactions of any type that are missing the onset time: TEAEs that are missing the AE start time, occur on the day of an infusion and meet one of the following criteria:
 - SMQ Angioedema (broad)
 - SMQ Hypersensitivity (broad)
 - SMQ Hypertension (narrow)
 - SMQ Anaphylactic reactions - meet any of the 3 criteria from Section 2.6.3 of the Introductory Guide for SMQs ([MedDRA, 2017](#)):
 - A narrow term or a term from Category A
 - A term from Category B AND a term from Category C
 - A term from Category D AND [a term from Category B OR a term from Category C]
 - HLTs: “Rashes, eruptions and exanthems NEC”, “Erythemas”, “Pruritus NEC”
 - PTs: Pyrexia, Flushing, Feeling hot, Chest pain, Chest discomfort, Myalgia, Myalgia intercostal, Back pain, Dizziness
- Potential infusion-related reactions excluding those of an anaphylactic nature that are missing the onset time: TEAEs that are missing the AE start time, occur on the day of an infusion and meet one of the following criteria:
 - SMQ Angioedema (broad)
 - SMQ Hypersensitivity (broad)
 - SMQ Hypertension (narrow)
 - HLTs: “Rashes, eruptions and exanthems NEC”, “Erythemas”, “Pruritus NEC”
 - PTs: Pyrexia, Flushing, Feeling hot, Chest pain, Chest discomfort, Myalgia, Myalgia intercostal, Back pain, Dizziness
- Anaphylactic reactions that are missing the onset time: TEAEs that are missing the AE start time, occur on the day of an infusion AND meet any one of the 3 criteria from Section 2.6.3 of the Introductory Guide for Standardised MedDRA Queries (SMQs) ([MedDRA, 2017](#)):

- A narrow term or a term from Category A
- A term from Category B AND a term from Category C
- A term from Category D AND [a term from Category B OR a term from Category C]

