#### 7.1.3.4.4 Pharmacodynamic Markers

#### 7.1.3.4.5 Safety

##### 7.1.3.4.5.1 River Vision TED01RV Study

Treatment-emergent AEs (TEAEs) in TED01RV that were reported for at least 5% of the subjects in the teprotumumab group and had a greater frequency than that in the placebo group are shown in [Table 7.2](#). The majority of AEs were mild, required no treatment, and resolved while subjects remained on drug. Hyperglycemia, which was monitored by assessing blood glucose and HbA1c, was the only AE clearly identified as related to study drug.

**Table 7.2 Summary of TEAEs Reported in at Least 5% of Subjects in Teprotumumab Treatment Group and % is Greater Than Placebo**

TEAEs	Placebo N=44 n (%)	Teprotumumab N=43 n (%)	Summary Details for TEAEs in Teprotumumab Group
Any TEAE	32 (72.7)	32 (74.4)	
Nausea	4 (9.1)	8 (18.6)	Generally mild and reported after first/second infusions
Muscle spasms	2 (4.5)	8 (18.6)	Intermittent, 2/8 cases experienced for >1 week and treated with muscle relaxants
Diarrhea	2 (4.5)	6 (14.0)	Treatment required in 2/6 cases, 1 designated an SAE (see below)
Hyperglycemia	2 (4.5)	5 (11.6)	Mechanism-based AE
Alopecia	2 (4.5)	3 (7.0)	All mild and no treatment required
Dry skin	0	3 (7.0)	All mild, one case used topical dry skin cream
Dysgeusia	0	3 (7.0)	For 2/3 cases a transient “metallic” taste on Days 1-2
Headache	2 (4.5)	3 (7.0)	Generally mild, one subject took paracetamol
Paresthesia	0	3 (7.0)	“Tingling” reported in nose, feet or chest; variable onset and in 2/3 cases occurred on 1 day
Hearing impaired	0	3 (7.0)	Disparate symptoms, onset and duration (i.e., one unilateral with onset 16 weeks after end of therapy, one mild bilateral that resolved, one intermittent in a subject with positive history of tinnitus)
Weight loss	0	3 (7.0)	Variable timing; decreases range from 5-9 lb.

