#### **9.5.4.1.2 Documentation of Adverse Events**

Adverse events that are ongoing at the completion of HZNP-TEP-301 and/or occur prior to dosing on Day 1 will be considered pre-dose AEs. The TEAE reporting period begins with administration of the first dose of study medication on Day 1 and continues until 3 weeks after the last dose of study drug, and the Follow-Up AE reporting period begins 3 weeks after the last dose of study drug through completion of the Follow-Up Period (Month 12 or PW). All pre-dose AEs, TEAEs, and AEs during the Follow-Up Period must be recorded in the source documents and in the subject's eCRF.

If the Investigator observes an SAE after study completion that he/she believes was possibly caused by the study medication, the Investigator will report this SAE using the procedures described in [Section 9.5.4.1.5](#).

Detailed information regarding all SAEs must also be recorded on the Serious Adverse Event Reporting Form. Whenever possible, the Investigator should group together into a single term the signs and symptoms that constitute a single diagnosis. For example, cough, rhinitis, and sneezing might be grouped together as "upper respiratory infection" if the Investigator is confident of the diagnosis.

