3.5. DETERMINATION OF SAMPLE SIZE

The sample size is not based on statistical considerations. Subjects who are proptosis non-responders at Week 24 of HZNP-TEP-301 or who are proptosis responders at Week 24 but meet the criteria for re-treatment due to relapse during the Follow-Up Period of HZNP-TEP-301 will be eligible for enrollment.

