6.2.3. Study Baseline and HZN-001 Baseline

The following two definitions of baseline will be utilized for analysis purposes:

- **Study Baseline** will be defined as the last measurement taken prior to first dose in HZNP-TEP-302 (considering unscheduled visits when available). If a Study Baseline value is not obtained in the HZNP-TEP-302 study prior to dosing, the last value measured in HZNP-TEP-301 will be used. Study Baseline comparisons will be provided for all applicable endpoints.
- **HZN-001 Baseline** will be defined as the last measurement taken prior to first dose of HZN-001 whether it occurred in HZNP-TEP-301 or HZNP-TEP-302 (considering unscheduled visits when available). HZN-001 Baseline comparisons will be provided for select assessments of safety, i.e. laboratory assessments, vital signs, ECGs, physical examinations, and ophthalmic examinations.

Change from (Study or HZN-001) Baseline will be defined as the measurement at each time point minus the relevant Baseline value.

The primary objective will be assessed using the Study Baseline.

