14.3.1.2.2	Treatment-Emergent Adverse Events by System Organ Class and Preferred Term During the Treatment Period, Subgroup Analysis by Age Group	ITT
14.3.1.2.3	Treatment-Emergent Adverse Events by System Organ Class and Preferred Term During the Treatment Period, Subgroup Analysis by Gender	ITT
14.3.1.2.4	Treatment-Emergent Adverse Events by System Organ Class and Preferred Term During the Treatment Period, Subgroup Analysis by Race	ITT
14.3.1.2.5	Treatment-Emergent Adverse Events by System Organ Class and Preferred Term During the Treatment Period, Subgroup Analysis by Ethnicity	ITT
14.3.1.3.1	Treatment-Emergent Adverse Events by System Organ Class, Preferred Term and Maximum Intensity During the Treatment Period	ITT
14.3.1.3.2	Adverse Events by System Organ Class, Preferred Term and Maximum Intensity During the Follow-Up Period	ITT

14.3.1.4.1	Treatment-Related Treatment-Emergent Adverse Events by System Organ Class and Preferred Term During the Treatment Period	ITT
14.3.1.4.2	Treatment-Related Adverse Events by System Organ Class and Preferred Term During the Follow-Up Period	ITT
14.3.1.5.1	Serious Treatment-Emergent Adverse Events by System Organ Class and Preferred Term During the Treatment Period	ITT
14.3.1.5.2	Serious Adverse Events by System Organ Class and Preferred Term During the Follow-Up Period	ITT
14.3.1.6	Treatment-Emergent Adverse Events Leading to Permanent Withdrawal of Study Drug by System Organ Class and Preferred Term During the Treatment Period	ITT
14.3.1.7.1	Treatment-Emergent Adverse Events of Special Interest by System Organ Class and Preferred Term During the Treatment Period	ITT
14.3.1.7.2	Treatment-Emergent Adverse Events of Special Interest with a Missing Onset Time by System Organ Class and Preferred Term During the Treatment Period	ITT
14.3.1.7.3	Adverse Events of Special Interest by System Organ Class and Preferred Term During the Follow-Up Period	ITT
14.3.1.8.1	Treatment-Related Treatment-Emergent Adverse Events by System Organ Class, Preferred Term and Maximum Intensity During the Treatment Period	ITT
14.3.1.8.2	Treatment-Related Adverse Events by System Organ Class, Preferred Term and Maximum Intensity During the Follow-Up Period	ITT
14.3.4.1.1.1.1	Summary and Change from Study Baseline in Hematology Laboratory Test Results	ITT
14.3.4.1.1.1.2	Summary and Change from HZN-001 Baseline in Hematology Laboratory Test Results	ITT
14.3.4.1.1.2.1	Hematology Laboratory Test Results Shift from Study Baseline	ITT

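### The SAP defines every AESI as a treatment-emergent event, which conflicts with its own planned Follow-Up AESI table and would leave that table essentially empty if programmed as defined

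*SAP*

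**What the plan says.** **Definition.** SAP 10.3.1 is the only place where AESIs are defined for analysis. Each of its nine entries is restricted to TEAEs, for example "Hearing loss: TEAEs by any PTs under the SMQ".

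**Window.** Under SAP 10.3 the TEAE period starts with the first HZNP-TEP-302 dose and "continues until 3 weeks (21 days) after the last dose of study drug". The Follow-Up AE period opens at that same point. Footnote 22 to the Schedule of Assessments (SAP 3.8, Protocol 2.1) classes events that start or worsen during Follow-Up as postdose AEs, separate from TEAEs.

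**Planned output.** SAP 10.3, after listing the TEAE summaries (the AESI summaries among them), says: "The aforementioned summaries will be repeated for AEs occurring during the Follow-Up Period". Only the summary of withdrawals from study drug is excepted. SAP 16 accordingly lists Table 14.3.1.7.3, "Adverse Events of Special Interest by System Organ Class and Preferred Term During the Follow-Up Period". SAP 18 adds one AESI listing, 16.2.7.5.

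**Events carried over from the lead-in.** Protocol 9.5.4.1.2: "Adverse events that are ongoing at the completion of HZNP-TEP-301 and/or occur prior to dosing on Day 1 will be considered pre-dose AEs". The same section requires them in the eCRF. Footnote 22 makes them TEAEs if they worsen after Day 1 dosing.

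**The concern.** A programmer who derives one AESI flag from 10.3.1 and then restricts it to Follow-Up events will find almost nothing. An event that starts after the TEAE window cannot satisfy a definition that requires a TEAE. A reader of the report could then take an empty Table 14.3.1.7.3 as evidence that no AESI occurred off treatment.

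Hearing loss shows why this matters. Protocol Table 7.2 (section 7.1.3.4.5.1) reports three hearing events on teprotumumab in the earlier placebo-controlled study, "one unilateral with onset 16 weeks after end of therapy". An event with that timing would fall outside the SAP's AESI definition.

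There is a smaller gap at the other end. An AESI still present at Day 1 and not worsening is a pre-dose AE, and no planned table shows pre-dose AEs.

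**Working it through.** No power or event-count input bears on this point: the study is descriptive and "The sample size is not based on statistical considerations". The check compares definitions, windows and table titles.

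**1. The definitions.** Four of the nine entries are by term only: hyperglycemia, muscle spasm, diarrhea and hearing loss. Five are tied to an infusion: potential infusion-related reactions, anaphylactic reactions, and three versions for missing onset times. All nine require a TEAE.

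**2. Overlap of the two windows.** Under SAP 10.3 the TEAE and Follow-Up periods share only the 21st day after the last dose. Footnote 22 instead runs TEAEs to the end of the Treatment Period, so the overlap can be longer. For a fully dosed subject, using the visit windows in SAP Table 1:
- Last infusion, Week 21: Day 148 ± 3, so last dose + 21 falls on Day 166 to Day 172.
- Week 24 visit: Day 169 ± 7, so Day 162 to Day 176.
- Largest overlap: 176 − 166 = 10 days.

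On either reading almost all of Follow-Up lies outside the TEAE window.

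**3. Share of AE observation affected.** SAP 6.4 gives target days of 148 (Week 21), 169 (Week 24) and 337 (Week 48).
- TEAE window closes: 148 + 21 = Day 169.
- Follow-Up remaining: 337 − 169 = 168 days.
- Share: 168 / 337 = 0.499, about 50%.

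This applies to lead-in proptosis non-responders. Relapse subjects have no Follow-Up Period (SAP 3.4).

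**4. The late hearing event.** Sixteen weeks is 16 × 7 = 112 days. Counted from the last infusion, onset would be 148 + 112 = Day 260; from Week 24, 169 + 112 = Day 281. Both fall within Follow-Up.

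**5. What Table 14.3.1.7.3 would contain.**

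| Reading | Four term-based categories | Five infusion-timed categories |
|---|---|---|
| 10.3.1 as written (TEAEs) | essentially empty | essentially empty |
| 10.3 and the table title (AEs) | can be filled | empty, because no infusions are given in Follow-Up |

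**6. Where the events appear otherwise.** Table 14.3.1.2.1.2 gives all Follow-Up AEs by system organ class and preferred term, so a late hearing event is still tabulated under its own term.

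**7. Carried-over events.** Planned tables in SAP 16 that show an unworsened AESI ongoing from the lead-in: none. The listing of all AEs covers it. SAP 6.2.3 says "HZN-001 Baseline comparisons will be provided for select assessments of safety" and names laboratory tests, vital signs, ECGs and examinations, but not AEs. Exposure is combined across both studies (Table 14.3.4.5.1.2), with no AE counterpart.

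**The case against.** **The intent is clear enough.** SAP 10.3 applies the repeated summaries to AEs. The title of Table 14.3.1.7.3 omits the treatment-emergent label that Tables 14.3.1.7.1 and 14.3.1.7.2 carry. SAP 10.3 also has TEAEs flagged on every listing, which would be pointless on the AESI listing if AESIs were TEAEs by definition. The table mock-ups, which might settle the matter, are in a separate file (SAP 19). This stands. A reader might infer that the plan makes the Follow-Up table empty by rule; the documents show two texts in conflict, one of which clearly means the table to be filled. It does not remove the need for a correction, because 10.3.1 is the only definition a programmer has.

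**Nothing is lost from the report.** True for Follow-Up events, given the general table. What would be lost is their identification as AESIs.

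**Carried-over events belong to the lead-in study's reporting.** This largely stands. A reader might infer that persistent first-course events vanish from the HZN-001 column alone and make re-treatment look safer. The documents do not support that:
- The pre-dose rule applies to both lead-in columns. Protocol Table 7.2 shows muscle spasms, hyperglycemia and diarrhea on placebo too, each in 2 of 44 subjects (4.5%).
- Worsened events count as TEAEs under footnote 22, although SAP 10.3 does not repeat this.
- Glucose is already shown as a shift from HZN-001 Baseline by grade (Table 14.3.4.1.2.3.2).
- The documents give no count of events ongoing at Day 1, and the earlier study's account does not suggest frequent persistence. Only 2 of 8 subjects had muscle spasms for more than a week (Protocol 7.1.3.4.5.5.1). Hyperglycemia was back at baseline levels after treatment (7.1.3.4.1). Of the three hearing events, one resolved, one was intermittent and one began long after therapy.

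The column is meant to report events emerging on HZNP-TEP-302 treatment. At-risk denominators or a cumulative count would be a preference, and their absence is not an error.

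**Conclusion.** The conflict is real and should be resolved before programming. All nine AESI definitions require a TEAE, while a Follow-Up AESI table is planned with no other definition. Applied literally, that table and the non-TEAE part of the AESI listing would be essentially empty. The period concerned is about half of AE observation for a lead-in non-responder who receives all infusions and attends on target days; it does not exist for relapse subjects. The effect is on the labelling of late events as AESIs, since the general Follow-Up table still shows them.

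Understatement of AESIs in the re-treated column is not shown. What can be said is narrower: unworsened AESIs carried over from HZNP-TEP-301 can be found in listings but in no planned table, and their number cannot be derived from the documents.

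**What to change.** In SAP 10.3.1:
- Define hyperglycemia, muscle spasm, diarrhea and hearing loss by their term lists on all AEs.
- Apply the period flag (pre-dose, treatment-emergent, Follow-Up) as a separate step. Table 14.3.1.7.1 then takes the treatment-emergent events, Table 14.3.1.7.3 the Follow-Up events, and Listing 16.2.7.5 all of them with the flag shown.
- State that the five infusion-timed categories do not apply in Follow-Up, so that their absence there is not read as a finding.

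Optional and cheap: add a row by lead-in treatment, for instance in Table 14.3.1.7.1, counting subjects with each term-based AESI ongoing at HZNP-TEP-302 Day 1.

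The cost is a change of wording, a check of the mock-ups and at most a few extra rows. No new data are needed, because the protocol already requires pre-dose, treatment-emergent and Follow-Up AEs in the eCRF.

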#### **9.4.6.3.2 Dose Modifications, Interruptions, and Delays**

Subjects will be monitored for immediate infusion-associated events (e.g., nausea, vomiting, facial flushing, warmth, dyspnea, dizziness, hypertension, hypotension, pruritus) and delayed infusion-associated events (e.g., rash). If immediate infusion-associated events are noted, the infusion rate will be slowed or interrupted, symptomatic treatment (e.g., antipyretics, antihistamines, beta-agonists, oxygen, IV fluid) will be administered, and vital signs (temperature, blood pressure, pulse, and respiratory rate) will be monitored every 5 minutes until stable and then every 15 minutes for 2 additional determinations. The infusion may be restarted upon complete resolution of symptoms; however, study drug dosing will be permanently discontinued if the event is an anaphylactic reaction.

If delayed infusion-associated events are noted, subjects may continue dosing at the Investigator's discretion; however, if a rash worsens following repeated dosing or other signs of serum sickness (e.g., delayed fever, myalgias, arthralgias) are present, study drug dosing will be permanently discontinued.

Following the appearance of either immediate or delayed infusion-associated events, subsequent doses may be pre-treated with diphenhydramine (1 to 1.25 mg/kg IV; maximum of 50 mg), ranitidine (50 mg IV), famotidine (0.5 mg/kg IV), dexamethasone (0.4 mg/kg IV; maximum of 20 mg), and/or acetaminophen (500 mg). All subsequent infusions will be administered over approximately 90 minutes (but not less than 80 minutes) with vital signs monitored every 15 minutes from the start of the infusion through 60 minutes after infusion completion.

In general, the decision to continue dosing should take into consideration the potential benefit and risk to a subject.

Any severe drug-related AE must revert to mild or moderate in intensity at least 2 weeks prior to the next scheduled dose in order for the dose to be administered; if the AE remains severe in intensity within 2 weeks of the next scheduled dose, the subject will be withdrawn from treatment.

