#### **9.5.4.1.1.5 Adverse Events of Special Interest**

Based on previous clinical experience in TED, the following AESIs are identified for this study (See [Section 7.1.3.4.5.5](#) for further information):

- Infusion reactions (e.g., nausea, vomiting, facial flushing, warmth, dyspnea, dizziness, hypertension, hypotension, pruritus)
- Hyperglycemia
- Muscle spasms
- Diarrhea

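### The SAP's missing-onset-time definitions of infusion-related reaction do not name nausea, vomiting, dyspnea or hypotension, so untimed events of these types may go uncounted in Table 14.3.1.7.2

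*SAP*

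**What the plan says.** Protocol 9.5.4.1.1.5 lists the AESIs and illustrates the first of them: "Infusion reactions (e.g., nausea, vomiting, facial flushing, warmth, dyspnea, dizziness, hypertension, hypotension, pruritus". Protocol 9.4.6.3.2 uses the same nine examples for "immediate infusion-associated events (e.g., nausea, vomiting, facial flushing, warmth, dyspnea, dizziness, hypertension, hypotension, pruritus".

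SAP 10.3.1 turns this AESI into two rules.

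- **Onset time known:** "Potential infusion-related reactions: TEAEs that occur within 2 hours after initiating infusion". There is no term filter.
- **Onset time missing:** "TEAEs that are missing the AE start time, occur on the day of an infusion and meet one of the following criteria". The criteria are the angioedema and hypersensitivity SMQs (both broad), "SMQ Hypertension (narrow"), three HLTs covering rashes, erythemas and pruritus, and nine preferred terms: "PTs: Pyrexia, Flushing, Feeling hot, Chest pain, Chest discomfort, Myalgia, Myalgia intercostal, Back pain, Dizziness".

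The missing-time rule has an any-type definition, which opens "Potential infusion-related reactions of any type that are missing the onset time: TEAEs that are missing the AE start time", and a definition that excludes anaphylactic events. The two share this list, except that the any-type definition also contains the anaphylactic SMQ algorithm. A third missing-time definition covers anaphylactic reactions alone and is not at issue here.

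The SAP's index of tables sends AESIs to Table 14.3.1.7.1 and those with a missing onset time to Table 14.3.1.7.2.

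**The concern.** The two rules can treat the same event differently. Nausea 30 minutes into an infusion is an AESI if a clock time was entered. The same nausea on the same infusion day without a time meets no named criterion.

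The four unnamed reactions are not marginal in the protocol. Besides the two lists of nine, Protocol 7.1.3.4.5.5.1 mentions all four (dyspnea as shortness of breath) among the symptoms that monoclonal antibody infusions may cause. Nor is the SAP list simply a narrow one: it adds chest pain, myalgia and back pain, which are not among the nine, and gives no reason for leaving these four out.

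The direction also runs against the SAP's own convention. Under SAP 6.3.4, a missing intensity becomes severe, a missing relationship becomes related, and an AE with no start date at all is treated as treatment-emergent unless its stop date rules that out. Here, missing information makes an event harder to count.

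What is at stake is whether Table 14.3.1.7.2, which exists to catch untimed events, catches reactions that the protocol itself names.

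**Working it through.** **Step 1. Match the nine protocol examples to the missing-time list, by name.**

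| Protocol example | Named criterion in SAP 10.3.1 (missing time) |
|---|---|
| Facial flushing | PT Flushing |
| Warmth | PT Feeling hot |
| Dizziness | PT Dizziness |
| Hypertension | SMQ Hypertension (narrow) |
| Pruritus | HLT Pruritus NEC |
| Nausea | none |
| Vomiting | none |
| Dyspnea | none |
| Hypotension | none |

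Named: 5 of 9. Not named: 9 − 5 = 4.

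**Step 2. Ask whether the four can enter another way.** Both definitions contain two broad SMQs, and the any-type definition adds the anaphylactic algorithm, which accepts some terms only in combination. The documents do not list the member terms of any of these. Capture of dyspnea or hypotension, for instance, can be neither shown nor excluded. The algorithm cannot help the definition that excludes anaphylactic events, because it is not part of it.

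**Step 3. Identify which outputs depend on the list.** The list applies only to TEAEs with no start time. It therefore shapes Table 14.3.1.7.2 and leaves the timed rule behind Table 14.3.1.7.1 unchanged. An untimed nausea event still appears in the TEAE table by SOC and PT (14.3.1.2.1.1), in the intensity table, in the relatedness tables where it is judged related, and in the full AE listing (16.2.7.1).

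**Step 4. Size.** The plan states no AESI count and no rate of missing start times, so there is no figure to reproduce. The nearest number is in Protocol Table 7.2 for the earlier TED trial, where nausea occurred in 8/43 = 18.6% on teprotumumab and 4/44 = 9.1% on placebo, with the note "Generally mild and reported after first/second infusions". With muscle spasms, it was the joint most frequent teprotumumab TEAE in that table.

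For nausea alone, treating each affected subject as having one such event:

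subjects missed per 100 treated = 100 × (8/43) × f × m

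where f is the share of these subjects whose nausea falls on an infusion day and m is the share of those without a start time. Both are assumptions; I took f from 25% to 100% and m from 0 to 20%.

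| f | m = 0 | m = 5% | m = 20% |
|---|---|---|---|
| 25% | 0 | 0.23 | 0.93 |
| 50% | 0 | 0.47 | 1.86 |
| 100% | 0 | 0.93 | 3.72 |

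The range is 0 to 3.7 per 100, and about 0.5 at f = 50% and m = 5%.

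**The case against.** The strongest reply is that the two rules differ for good reason. With a known time, the 2-hour window supplies specificity; without it, a term list has to. That is fair, and different rules are not in themselves an error. It does not explain why the list leaves out these four while admitting terms the protocol never mentions as examples.

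Second, both protocol lists are illustrative, and Protocol 9.6 says that SAP analyses supersede those in the protocol. This stands: no requirement is breached. The point is one of consistency.

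Third, 8/43 is all nausea in the earlier trial, not untimed infusion-day nausea. Protocol 7.1.3.4.5.1 reports infusion-associated AEs there in one teprotumumab subject, with flushing, warmth, and raised heart rate and blood pressure; nausea is not mentioned. Some nausea is also background, as the placebo rate shows. All of this stands, and it is why the calculation in Step 4 is only an illustration.

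A reader might go further and infer that the AESI count is too low. The documents do not support that. The main table has no term filter, and the number of untimed events is unknown. The missing-time list can also over-count: it spans the whole infusion day and includes terms such as pyrexia and back pain. The net direction is therefore not known. Nor can one say that every untimed event of these types is lost, since broad SMQ contents cannot be checked and the events remain in the general TEAE tables.

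**Conclusion.** The point holds as a gap in a supplementary table. By name, four of the nine protocol examples are absent from both missing-time definitions, and the same event can be counted or not according to whether a clock time was entered. This conclusion rests on matching names, because the SMQ contents are not in the documents.

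The consequence is conditional. Untimed infusion-day nausea, vomiting, dyspnea or hypotension may go uncounted in Table 14.3.1.7.2. The loss is nil if all start times are recorded, and small under the assumed ranges for nausea. The other three reactions cannot be sized from the documents. The case for acting is that the correction is specific and nearly free, and brings the rule closer to the protocol's examples and to the conservative approach of SAP 6.3.4.

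**What to change.** In SAP 10.3.1, add the preferred terms nausea, vomiting, dyspnoea and hypotension to both the any-type and the non-anaphylactic missing-time definitions. If the sponsor finds that an SMQ already captures one of them, the addition does no harm, since SAP 10.3 counts a subject at most once per preferred term.

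In Table 14.3.1.7.2 or a footnote to it, report how many infusion-day TEAEs have no start time, so that a reader can judge whether the issue matters at all.

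The cost is a few lines of SAP text and a change to a programmed term list, with no new data. The downside is that some unrelated infusion-day events of these four types will be counted, but only in the separate missing-time table.

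Dropping the term filter and counting every untimed infusion-day TEAE would remove the inconsistency altogether. It would also label clearly unrelated events on any of up to eight infusion days as potential reactions. That is a debatable trade-off, and closing this gap does not require it.
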